Electrical Stimulation as an Adjunctive Therapy to Increase Vascular
Perfusion in People With PAD or PVD

Study Protocol and Statistical Analysis Plan

NCT04313985

September 12, 2018

Study Title

Electrical stimulation as an adjunctive therapy to increase vascular perfusion and enhance healing in patients with chronic wounds associated with peripheral arterial disease: A prospective case-controlled double-blinded randomized cross-over pilot study.

OBJECTIVES (Primary & Secondary Outcome measures)

Primary Objective:

This study is designed to test the effectiveness of the Tennant Biomodulator® PRO electrical stimulation device (Avazzia), which uses BEST™ (Bio-Electric Stimulation Technology), in enhancing short-term perfusion at the wound site in patients with chronic wounds associated with peripheral arterial disease. The perfusion will be examined using the HyperMed's HyperView device.

Secondary Objectives:

This study is also designed to test the effectiveness of Avazzia in reducing bacterial burden at the wound site, enhancing overall wound healing, and improving patient's pain level. The bioburden and bacterial load will be assessed using quantitative deep tissue swabs from the wounds. Wound healing will be assessed by percentage decrease in wound size. Pain will be assessed using a numerical 0-10 visual scale.

BACKGROUND

Study Disease:

Chronic cutaneous wounds are defined as wounds that have failed to proceed through an orderly and timely series of events to produce a durable structural and functional closure. The main etiologies include diabetes, pressure, venous insufficiency, and peripheral arterial disease. Those afflicted experience decreased quality-of-life, pain, restricted mobility, loss of limb, and loss of life. The incidence is on the rise due to aging population and growing prevalence of obesity and diabetes. Approximately, 2% of the population in developed countries suffer from chronic wounds, and the care costs in the United States alone exceed \$50 billion annually. Peripheral arterial disease constitutes estimated 20% of the chronic wounds. Arterial ulcers, also referred to as ischemic ulcers, are caused by poor perfusion (delivery of nutrient-rich blood) to the lower extremities. The overlying skin and tissues are then deprived of oxygen, killing these tissues and causing the area to form an open wound. In addition, the lack of blood supply can result in minor scrapes or cuts failing to heal and eventually developing tissue necrosis and/or ulceration. The primary goal of the treatment for arterial ulcers is to increase circulation to the area, either surgically or medically. Surgical options range from revascularization in order to restore normal blood flow to amputation and rehabilitation in extreme cases. It is needless to say that the surgical options are invasive and associated with high risk. As for non-surgical measures, modifying contributing factors can slow or stop the progression of the local ischemia. Additionally, there are boots and pumps available to augment perfusion to the affected limb. There is an apparent lack of effective non-surgical modality to treat this crippling health condition.

Study Devices:

* Tenant Biomodulator PRO electrical stimulation device (Avazzia): This study is designed to test the effectiveness of the Avazzia device, which uses BEST™ (Bio-Electric Stimulation Technology), in enhancing short-term perfusion at the wound site. Avazzia device is a microcurrent transcutaneous electro-stimulation device with proprietary frequency sets specified by [name] within the BEST platform control options. It is an easy-to-use, hand-held, AA battery-operated portable device for use at home or clinic. It applies charge and power to the tissue through electrodes where maximum power delivered to the load is controlled and limited, and an automatic shut off is implemented. The user can passively place the electrodes where indicated and apply stimulation for a set period of time. The user controls the output by selecting the preset mode and power setting. BEST™ devices produce unique microcurrent impulses transmitted through the skin to interface with the internal peripheral nervous system for the purpose of therapeutic intervention. With each response, the electrical properties of the tissue change. These changes in the tissue characteristics result in changes in the output. The device detects changes and indicates relative tissue reaction responses in a cybernetic feedback loop. BEST products are controlled by a high-performance micro-computer chip, which uses Avazzia proprietary software. These hand-held devices are FDA-cleared for the symptomatic relief and management of chronic, intractable pain. Additionally, there is data to suggest their effect in improving perfusion, as well as their disinfectant properties.

* We will examine perfusion using the HyperMed's HyperView device: HyperView is a handheld, battery operated, portable diagnostic imaging device that is used to assess tissue oxygenation without contacting the patient. Patented technology uses a proprietary spectrometer to measure light absorption in blood molecules to determine levels of oxyhemoglobin and deoxyhemoglobin and oxygen saturation in superficial tissue. The product is intended for use by physicians and healthcare professionals as a non-invasive tissue oxygenation measurement system that reports an approximate value of oxygen saturation (O₂Sat), oxyhemoglobin level (Oxy), and deoxyhemoglobin level (Deoxy) in superficial tissue. The HyperView system displays two-dimensional, color-coded images of tissue oxygenation of the scanned surface. Images and data provide hyperspectral tissue oxygenation measurements for selected tissue regions. The product is indicated for use to determine oxygenation levels in superficial tissues for patients with potential circulatory compromise.

For Clinicaltrials.gov Compliance:

The devices used in our study are both FDA-cleared.

Rationale:

It has been proven that improving arterial supply in patients with peripheral arterial disease would enhance the healing process of the associated wounds in this patient population. The preliminary data suggests that electric stimulation may enhance vascularization. Therefore, we hypothesize that electric stimulation may be beneficial in healing the wounds associated with peripheral arterial disease. We hypothesize that, based on previous data, Avazzia would enhance short-term perfusion, decrease bioburden, decrease pain, and improve overall wound healing. The scientific premise is supported by previous literature including those published by

[name]R. Nair.

Study Design:

- * The primary purpose for the study is “treatment”.
- * The interventional model is “cross-over” where participants will receive one of two alternative interventions during stage 1 and the other in stage 2.
- * There will be “two” intervention arms in this study.
- * The study will be masked in a “double-blind” fashion, as both parties will be unaware of intervention assignment.
- * The study will be “randomized”.
- * The primary outcome that the study is designed to evaluate is “efficacy”.

Inclusion Criteria

- * Age above 18 years
- * Ankle Brachial Index (ABI) ≤ 0.7
- * Chronic wounds associated with peripheral arterial disease.
- * Failure to demonstrate clinically-significant healing after 4 weeks of conventional therapy.
- * Subjects must demonstrate ability to understand and the willingness to sign a written informed consent document.
- * Wound size $\leq 5\text{cm}$ diameter at widest point.
- * We will include patients with clinical malnutrition but subject this data to subgroup analysis.

Exclusion Criteria

- * Age younger than 18 years
- * ABI > 0.7
- * Wound size $> 5\text{cm}$ diameter at widest point
- * Active malignancy
- * Clinical signs of infection at the wound site.
- * Patients in need for immediate surgical revascularization including those with critical limb ischemia and/or wet gangrene.

Informed Consent Process

All participants will be provided a consent form describing the study with sufficient information for participants to make an informed decision regarding their participation. Participants must sign the IRB approved informed consent prior to participation in any study specific procedure. The participant will receive a copy of the signed and dated consent document. The original signed copy of the consent document will be retained in the research file.

Randomization Procedures

Upon enrollment, each patient will be randomized via sealed envelopes to one of the two study groups, treatment group and control group. The randomization process will be conducted by an independent clinic staff. Both patients and primary investigators will be blinded to the randomization status.

Study Timeline

Primary Completion:

The study will reach primary completion 6 months from the time the study opens to accrual.

Study Completion:

The study will reach study completion 7 months from the time the study opens to accrual.

TREATMENT PLAN

Study Design

To validate our hypotheses, we will conduct a prospective case-controlled double-blinded randomized cross-over pilot study. We plan to enroll total of 30 patients, 15 in the study group and 15 in the control group. All subjects will be assessed during the screening period for inclusion and exclusion criteria. Patients will be followed for total of two weeks. Patients will visit the wound clinic twice during the follow-up period for assessing outcomes, one week and two weeks after the initial enrollment. Study protocol consists of 5 steps:

- Step 1 (Take BEFORE-treatment data): document the wound size; take perfusion data before-treatment (using HyperView device); take a wound swab for bacterial measurement (tissue samples will not be retained and will not be used for future research); document the pain level; take a photograph of the wound.
- Step 2 (Apply study treatment protocol therapy): First, test the device and equipment before treating the patient. Verify the device, conductive electrode pads, and lead wires connections by letting the patient feel what the stimulation will feel like by placing the electrode pads on the hands of the patient, powering on the device, and increasing the power until the stimulation is felt. Then, turn off the device and move the pads to the treatment area on the patient. Explain to the patient that it is normal for some patients to not feel the stimulation due to the chronic condition of their wound. It is also normal for some patient's skin to become more sensitive during therapy so that while they may not feel the stimulation at first, it is possible that they will begin to feel it, and it may even become too strong and need to reduce the intensity power settings. The patients can do this themselves if the output becomes uncomfortable. Treat the patient's wound area as the following. Place self-adhesive, conductive electrode pads on either side of the wound on the skin where the pads are not placed in the open wound itself, but rather in the surrounding area with one pad on each side of the wound. Connect the pads to the lead wire to the Avazzia device. There will be two different sets of lead wires marked as A or B where A is for "good" lead wires for therapy and B is for "broken" lead wires for the control group. Turn on the Avazzia device and change modes to the **RSI** mode. Allow to run unattended for 15 minutes. Change modes to **Blue Stimulation** mode without moving any of the pads. Allow to run unattended for 10 minutes. The total duration of each treatment session per day will be 25 minutes.
- Step 3 (Take AFTER-treatment data): take perfusion data after-treatment; take a wound swab for bacterial measurement; document the pain level; take a photograph of the wound

- Step 4: One week later, patient assigned groups will be switched. The study will be repeated with cross-over fashion so that the patients that had real treatment repeat the test, but with broken lead wires. And patients who had broken lead wires get treatment with good lead wires.
- Step 5 (Take final data one week later): document the wound size; take perfusion data; take a wound swab for bacterial measurement; document the pain level; take a photograph of the wound

Criteria for Removal from Study

In the case of following events, the patient will be removed from the study and his or her usual care will be restored based on the conventional therapy: disease progression; unacceptable adverse events; patient withdrawal from study.

Alternatives

Patients in both study and control groups will continue to receive the standard-of-care wound therapy throughout the course of study.

Potential Adverse Events

Potential risks associated with Avazzia device is minimal, being limited to pain at the site of probe application, and/or temporary numbness of the peri-wound area.

Potential risks associated with HyperView device is negligible.

Potential risks associated with wound swabs is minimal, being limited to pain and/or minimal bleeding.

STATISTICAL CONSIDERATIONS

Assuming a 1-2% drop out, the estimated sample size is 30. The sample size will include a cross-over study design. We recognize that this sample size may not be sufficient to validate all primary and secondary end-points but would be sufficient to estimate trend and determine a more-accurate sample size for the larger scale study. A sample size for long-term benefit has not been calculated yet. This is a pilot study assessing improved perfusion. If findings demonstrate favorable trend, Avazzia will consider a larger study with appropriate sample size calculations consistent with assessment of long-term benefits.

Publication plans envisioned for this work

Results will be disseminated in relevant conferences (e.g. Wound Healing Society Annual Meeting) and peer reviewed journals (e.g. Wound Repair and Regeneration)

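### The trial is called double-blind, but Step 2 marks the lead wires with one fixed A/B code and prints its meaning, so the masking is exposed, though not shown to fail

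*Combined protocol and SAP*

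**What the plan says.** The Study Title, the Study Design list and the Study Design paragraph of the TREATMENT PLAN all call the trial double-blind. Randomization Procedures has sealed envelopes, independent clinic staff to run the process, and patients and primary investigators kept unaware of allocation.

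Step 2 of the TREATMENT PLAN describes the sham. There are two sets of "lead wires marked as A or B where A is for 'good' lead wires for therapy and B is for 'broken' lead wires", the second being for control. No patient-specific code, concealed key or relabelling between periods is described. Step 4 then switches everyone: "the patients that had real treatment repeat the test, but with broken lead wires", and the reverse for the other group.

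Step 2 opens with a test on the patient's hands: "Verify the device, conductive electrode pads, and lead wires connections by letting the patient feel what the stimulation will feel like". The test proceeds by "powering on the device, and increasing the power until the stimulation is felt". Next comes "Then, turn off the device and move the pads to the treatment area on the patient". Patients are also prepared for a lack of sensation: "Explain to the patient that it is normal for some patients to not feel the stimulation due to the chronic condition of their wound". After the pads are placed around the wound, a separate instruction follows: "Connect the pads to the lead wire to the Avazzia device". The A and B sets are introduced only after that.

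Step 3 lists the post-treatment data ("take perfusion data after-treatment; take a wound swab for bacterial measurement; document the pain level; take a photograph of the wound") without naming who takes them. Steps 1 and 5 name no one either.

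**The concern.** A sham control protects the comparison only if the people who produce and record the outcomes cannot tell sham from active. Here the two conditions are told apart by a visible letter, and the meaning of the letter stands in the instructions for running the session. The mark conceals nothing from a person who has read them. In a cross-over the disclosure doubles, since knowing one period gives the other.

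At stake is the active-minus-sham contrast that the pilot is meant to describe. Perfusion, the primary outcome, is read by a non-contact instrument. However, the Study Devices section says its values are reported for selected regions of tissue, and the plan does not say who selects them. Pain is rated by the patient, so it depends more on whether the patient can tell the sessions apart.

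The hand test raises a second, smaller question. It checks lead connections by whether the patient feels current, and does not say which lead is on the device at that moment.

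**Working it through.** The plan gives no figure on masking, so there is none to reproduce. The check sets the relevant sections side by side and counts the sessions exposed.

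**1. Who is meant to be unaware, and who handles or records.**
- Randomization Procedures names patients and primary investigators as blinded. It gives the independent staff the randomization process and no other task.
- Step 2 needs someone to connect the lead and, after 15 minutes, to change the mode with the lead still attached. No role is named for either task.
- Steps 1, 3 and 5 need someone to take the perfusion, swab and pain data, and in Steps 1 and 5 the wound size. No role is named.
- It is therefore unstated whether the person recording outcomes can see the lead.

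**2. What one look at a lead reveals.** Step 2 has two marked sets with one stated meaning. That the code is the same for every patient follows from this; it is not stated in those words.
- Inputs: 30 patients (Study Design in the TREATMENT PLAN); two treatment sessions each (Steps 2 and 4).
- Sessions: 30 × 2 = 60, before drop-out.
- Printed key: one look gives that session and, by the switch in Step 4, the other one, so 2 sessions.
- One look per patient: 30 × 2 = 60, all sessions.
- Patient-and-visit codes with the key withheld: a look gives 0 of 60. An accidental disclosure for one patient gives 2 of 60 and says nothing about the other 29 patients.

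**3. Which lead the hand test uses.** The order in Step 2 is: hand test, device off and pads moved, advice on sensation, pads placed at the wound, lead connected, sets A and B introduced, device on.
- *Working lead.* This fits the order, because the lead connection and the A/B sets come after the test. The patient feels the current whatever the allocation, and the test reveals nothing about it.
- *Assigned lead.* Assume that a broken lead carries no current. The test then cannot reach its end point in a sham session, and patient and operator both learn that it is sham.

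The first reading is the more natural. The text does not exclude the second.

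**The case against.** The strongest reply is that this is silence rather than contradiction. A protocol must define its sham somewhere. Sealed envelopes and independent staff are in place, and those staff could handle the leads out of the investigators' sight. An unblinded lead handler is compatible with everything written. Outcome data are taken after the 25-minute run, and nothing says that the assessor sees the lead. HyperView reports measured values, and region selection is mentioned only in a product description. Patients are told that feeling nothing can be normal.

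Much of this stands: the documents do not show that anyone is unblinded. It does not remove the point about the mark. The fixed code and its printed meaning are stated features of the procedure, and no provision keeps them from those who take the data. The advice to patients helps with sensation at the wound but does nothing about the code.

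A reader might infer three stronger things, none of which the documents support.
- *That the blinding fails.* The text shows exposure only.
- *That the hand test discloses sham, or that Step 2 leaves no point at which to change the lead.* Step 2 has a separate lead connection after the test, and on the natural reading the test is neutral.
- *That the pilot's effect is inflated by a calculable amount and a later study would be undersized.* The documents give no bias value. STATISTICAL CONSIDERATIONS says the pilot will inform a larger study's sample size, but ties that study's calculations to long-term benefit. It does not establish that the short-term perfusion estimate would be used directly.

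**Conclusion.** The concern holds as an exposure of the masking and should be fixed. One fixed, self-explaining mark lets an informed viewer identify both of a patient's sessions, up to 60 of 60 across the trial. The figure is a ceiling: it assumes that the viewer knows the procedure and sees a lead for each of the 30 patients. It is neither a probability nor an estimate of bias. If those who take outcomes never see the mark or do not know its meaning, there is no assessor bias from this source.

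The hand test is a secondary matter of clarity. It would unblind only if the assigned lead were used and a broken lead carried no current. Confidence is high that the code is printed and that no safeguard for assessors is stated. Whether masking would be lost in practice cannot be judged from the documents.

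**What to change.** 1. Remove the meaning of A and B from the working procedure. Label leads with patient-and-visit codes, with the key held only by the independent staff who already run randomization. They check each lead before issuing it.
2. State that whoever takes the perfusion, swab, wound-size and pain data has no access to the key, and that this covers any selection of HyperView regions.
3. State that the hand test uses one common working lead for every patient at both visits, and that the assigned coded lead is connected afterwards.
4. Describe patient blinding as partial when interpreting pain, since patients may feel a difference between sessions and the steps above do not prevent that.

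If the key cannot be kept from those taking outcomes, drop the double-blind label. Keeping lead handler and assessor separate, or covering the lead, would serve part of the same purpose; coded leads also limit an accidental disclosure to one patient.

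The cost is protocol wording, relabelled leads, one extra lead and a little time of existing staff to check and issue leads for about 60 sessions. Modes and run times are unchanged. The pre-issue check is needed because a common test lead does not check the assigned one.

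### Pain is listed for scoring after a wound swab that may itself hurt; scoring it before the swab would keep procedural pain out of a secondary outcome at almost no cost

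*Combined protocol and SAP*

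**What the plan says.** Under Secondary Objectives the measure is described in one sentence: "Pain will be assessed using a numerical 0-10 visual scale". No recall period is given, and nothing says whether the patient is to rate the wound or whatever is felt at that moment. The same section describes the swab: "The bioburden and bacterial load will be assessed using quantitative deep tissue swabs from the wounds".

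In the Treatment Plan the swab comes before the pain score each time the measurements are listed:

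- Step 1, before treatment, after a remark on sample retention: "tissue samples will not be retained and will not be used for future research); document the pain level; take a photograph of the wound".
- Step 3, after the 25-minute session: "take a wound swab for bacterial measurement; document the pain level; take a photograph of the wound".
- Step 5, final data: "Step 5 (Take final data one week later): document the wound size; take perfusion data; take a wound swab for bacterial measurement; document the pain".

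Step 4 has no list of its own. It repeats the test with the lead wires switched, so the same order recurs by implication. No interval between swab and score is given at any step.

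Potential Adverse Events says of the swab: "Potential risks associated with wound swabs is minimal, being limited to pain and/or minimal bleeding". For the stimulation device it lists "pain at the site of probe application, and/or temporary numbness of the peri-wound area".

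**The concern.** A pain score taken just after a procedure that can hurt may record the procedure as well as the wound. The trial wants to know whether stimulation relieves wound pain, and the protocol gives no instruction that would keep the two apart.

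Two consequences are possible. First, swab pain will vary between patients and occasions, which adds noise to every score. Secondly, if active stimulation dulls the reaction to the swab and the broken leads do not, part of an apparent pain benefit would be a milder response to the swab. Randomisation, blinding and the cross-over would not remove that part, because it goes with the active treatment.

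The pilot is meant to show trends and to inform the size of a later study. A shifted pain difference or an inflated standard deviation (SD) would carry into that planning. No score free of the immediate swab is collected, so the problem could not be corrected afterwards.

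**Working it through.** **The plan's own figure.** The only planning figure is the sample size of 30 with 1-2% dropout. It agrees with 29 evaluable patients (29/0.99 = 29.3 and 29/0.98 = 29.6, both rounded up to 30). No basis for 29 is given, and no SD or effect size is given for pain. The point below does not depend on it.

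**Model for the Step 3 score.** Let W be wound pain, S the pain added by the swab, d the true relief of wound pain from active treatment, and f the fraction of swab pain that active treatment blunts.

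- Sham: W + S
- Active: (W − d) + (1 − f)S
- Sham minus active: d + fS

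If f = 0, the swab term cancels exactly. It also cancels in before-after changes, because the Step 1 score follows a swab too. The cost is then noise only: if swab pain varies independently between occasions with variance v, the variance of the within-patient active-sham difference in Step 3 scores rises by 2v.

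If f is not 0, the contrast is off by fS.

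**Where f could differ from 0.** Only at Step 3 and its repeat, straight after the session. Step 1 precedes treatment in that period. Step 5 comes a week later, when a temporary effect is not expected. There the issue is mixing and noise.

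**Illustrative size.** The documents give neither S nor f. Because the swab risk is described as minimal, S is assumed to be 0.5 to 1 point and f 25% to 50%:

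| S | f | False difference fS |
|---|---|---|
| 0.5 | 0.25 | 0.125 |
| 0.5 | 0.50 | 0.25 |
| 1 | 0.25 | 0.25 |
| 1 | 0.50 | 0.5 |

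These values apply if every patient is affected. If one fifth were affected (also an assumption), they fall to 0.125 × 0.2 = 0.025 and 0.5 × 0.2 = 0.1 at the two ends.

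**What that could do to a test.** The documents specify no test on pain. Suppose a two-sided 5% z-test on the within-patient difference, n = 30, d = 0, and an SD of that difference of 1.5 to 2.5. With t = fS/(SD/√30), the rejection rate is Φ(t − 1.96) + Φ(−t − 1.96).

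- fS = 0.125: 0.06 to 0.07
- fS = 0.25: 0.09 to 0.15
- fS = 0.5: 0.20 to 0.45 (at SD 2, t = 0.5/0.365 = 1.37 and the rate is 0.28)
- fS = 0: 0.05

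**After the change.** With pain scored first, S leaves both Step 3 scores. Any pain R still felt from the Step 1 swab remains: sham = W + R, active = (W − d) + (1 − f)R, contrast d + fR. R has had at least the 25-minute session to fade, so fR should be smaller than fS. The listed order carries R as well, so the change does not introduce it.

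**The case against.** The strongest reply is that the steps are lists of data to collect, not a stated working sequence. No timing is given, so scoring immediately after the swab is an inference from the order. That stands, and the point is conditional on the listed order being followed. It is also a reason to state the order.

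A reader might infer that the swab must hurt by a different amount after active treatment than after sham. The documents do not support that. The numbness is a potential effect around the wound, while the swab is taken from the wound and the pads are kept off the open wound. No text says that swab pain changes. The differential part is a possibility only.

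A reader might also take "It is also normal for some patient's skin to become more sensitive during therapy" to mean that sensitised skin makes the swab hurt more and so hides real relief. In context, that sentence in Step 2 explains that patients may begin to feel the current during the session and may need to turn it down. It says nothing about a swab taken after the device is off.

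Larger figures, such as a false difference of 1 point or more, would need a swab effect of at least 2 points at f = 50%. That sits poorly with a risk described as minimal.

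Finally, pain is one of several secondary outcomes in a 30-patient pilot whose plan already concedes limited power. That limits the importance of the point but does not argue against a change that costs almost nothing.

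**Conclusion.** The point holds in a limited form. If the listed order is followed, the 0-10 score can mix wound pain with swab pain at every measurement. A constant swab effect cancels between active and sham and leaves added noise of unknown size. At Step 3 and its repeat, cancellation may be incomplete, because the protocol itself lists temporary numbness around the wound as a possible device effect. Whether that alters swab pain is not stated.

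The illustrative false difference of about 0.1 to 0.5 points rests entirely on assumed values for swab pain and blunting, and it shrinks in proportion to the share of patients affected. It shows that the order could matter, not that a bias of that size is expected. This is a low-stakes improvement to a secondary outcome; the primary perfusion outcome is unaffected.

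**What to change.** In Steps 1, 3 and 5, and in the repeat under Step 4, place the pain score before the swab, state that this order is fixed, and ask the patient to rate current wound pain on the 0-10 scale.

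The cost is a small wording change. It needs no extra visit, measurement or patient, and no bacterial data are lost because the swab is still taken.

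One limitation remains. Residual pain from the Step 1 swab could still reach the Step 3 score. It occurs under both conditions and should largely cancel in the active-sham contrast, but a before-after change within one condition would still contain it. The active-sham contrast is therefore the one to report for pain.

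### Removal for disease progression ends follow-up, so the week-2 wound size is lost in patients who may be healing poorly

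*Combined protocol and SAP*

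**What the plan says.** Criteria for Removal from Study lists three triggers. The rule and the first trigger read "the patient will be removed from the study and his or her usual care will be restored based on the conventional therapy: disease progression"; the other two are unacceptable adverse events and patient withdrawal. Disease progression is not defined anywhere. No section describes a measurement at or after removal, names an analysis set, or says how removed patients are analysed.

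The next section, Alternatives, states: "Patients in both study and control groups will continue to receive the standard-of-care wound therapy throughout the course of study".

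Healing is a secondary objective: "Wound healing will be assessed by percentage decrease in wound size". The final value comes from the last step of the Treatment Plan: "Step 5 (Take final data one week later): document the wound size". Clinic visits for outcomes are planned at one and two weeks after enrolment.

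Statistical Considerations gives the only figure for losses: "Assuming a 1-2% drop out, the estimated sample size is 30". It also describes the study's purpose: "This is a pilot study assessing improved perfusion".

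**The concern.** The rule does not separate two decisions: whether a patient receives further stimulation, and whether the patient is still measured. Read as written, both end together.

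If progression means that the wound is worsening, removal depends directly on the healing outcome. If it means worsening arterial disease, it is probably related to that outcome, because the Background attributes these ulcers to poor perfusion. In either case the missing week-2 wound sizes would come disproportionately from patients doing badly. A summary of those who finished would then tend to look better than the result in all randomized patients.

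There is also an inconsistency about care. Usual care is to be restored on removal, yet standard care is said to continue in both groups throughout, so it is unclear what was interrupted. This bears on the statistics, because it decides whether a wound size taken after removal reflects a change in care.

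**Working it through.** **What removal costs, by timing.** Step 1 documents wound size, Step 3 does not, and Step 5 does. If the repeat in Step 4 includes Steps 1 and 3, each patient has 3 wound sizes (Step 1, its repeat, Step 5). Perfusion, swab and pain have 5 readings each (Steps 1 and 3, both repeated, and Step 5).

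| Removed | Kept | Lost |
|---|---|---|
| After session 1, before session 2 | Baseline wound size; session-1 before and after readings | Step 5 wound size; the within-patient active-sham contrast for perfusion, swab and pain |
| After session 2, before week 2 | Both sessions' readings | Step 5 data only |

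**The plan's own figure.** The sample size of 30 cannot be reproduced, because no significance level, power, effect size or standard deviation is given. Only the drop-out step can be checked. 29/0.99 = 29.3 and 29/0.98 = 29.6 both round up to 30, so 30 is compatible with 29 evaluable patients, but 29 is not stated.

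**Expected losses at 1-2%.** The document does not say whether its drop-out figure includes removal for progression; it is applied to removals here as an assumption.
- Expected number: 0.01 × 30 = 0.3; 0.02 × 30 = 0.6.
- Chance of at least one among 30: 1 − 0.99^30 = 0.26; 1 − 0.98^30 = 0.45.

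**Effect on a completers-only summary.** The bias cannot be computed from the documents, so this is an illustration. Assume that completers' mean two-week change in wound size is −10%, and that removed patients would have averaged +g%, with g from 10 to 30. Let p be the share removed.

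Mean in all patients = (1 − p)(−10) + p·g = −10 + p(g + 10). The completer mean therefore overstates healing by p(g + 10) percentage points.

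| Share removed, p | g = 10 | g = 30 |
|---|---|---|
| 0.01 | 0.2 | 0.4 |
| 0.02 | 0.4 | 0.8 |
| 1/30 | 0.7 | 1.3 |
| 3/30 | 2.0 | 4.0 |

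The first two rows are averages over hypothetical trials, since 0.3 or 0.6 of a patient cannot be lost. A single trial has either no removal and no bias from this source, or at least the third row's effect. The last row is an assumption that the documents do not support, and 4.0 is its extreme corner.

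**The case against.** The strongest reply is that little of consequence is lost. The trial is a small perfusion pilot. By Step 5 every completer has had both real and sham sessions, so the pooled week-2 change does not estimate a treatment effect. At the plan's own drop-out figure the chance of no loss at all is 55% to 74%. Outcome visits fall only at weeks 1 and 2, so progression found at a visit coincides with a planned measurement, and silence about measuring at removal does not forbid it. Some removals will be for adverse events or withdrawal rather than poor healing.

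Most of this stands, and it limits the point. It does not remove it: a patient removed at week 1 still has no week-2 wound size under the rule, and nothing in the text confines removal to visit days.

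Four stronger readings are tempting and should not be drawn.

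- **That the primary result is biased.** The before and after perfusion readings of the first session are both in hand when a later removal occurs. The cost to perfusion is fewer second-session contrasts. The direction of any bias in an active-sham contrast depends on an analysis that the plan does not specify.
- **That the drop-out assumption is already refuted.** One removal is 1/30 = 3.3%, but any single loss among 30 exceeds 2%. That reflects the sample size and is not evidence against the assumption.
- **That removals will be frequent.** The inclusion criterion "Failure to demonstrate clinically-significant healing after 4 weeks of conventional therapy" might suggest so, but the exclusions cover clinical infection and "Patients in need for immediate surgical revascularization including those with critical limb ischemia and/or wet gangrene". Progression within two weeks may be uncommon, and no rate is given.
- **That the planning of the larger study is distorted.** The documents give no calculation from which this could be shown.

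**Conclusion.** The point holds in a limited form. Followed as written, the plan stops measuring patients who are removed for progression or adverse events. For progression, the lost week-2 wound size is plausibly related to the secondary healing outcome, and a completers-only summary would tend to overstate week-2 healing.

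The true size is unknown. It is likely small at the plan's 1-2%, at 0.2 to 0.8 points under the assumed means. That conclusion rests on three assumptions: that progression is related to wound worsening, that the drop-out figure describes removals, and that the analysis would be restricted to completers. None is stated in the plan.

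The change should be made because the data are obtainable at visits already scheduled. Confidence is medium, because the key term is undefined.

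**What to change.** Leave the clinical rule unchanged and separate it from follow-up.

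- State that receiving no further stimulation does not end follow-up. Unless consent is withdrawn, keep the planned week-1 and week-2 assessments, at minimum the non-invasive ones: wound size, perfusion, pain and photograph.
- Add no extra swab at removal. The plan itself lists pain and minor bleeding as swab risks.
- Flag values taken without the second session or after a change in care.
- Summarise healing in all randomized patients who have a week-2 value, keep first-period data from patients with one period only, and report removals by sequence, timing and reason.
- Reconcile the statement that usual care is restored on removal with the statement that standard care continues throughout. As a clarification, say what disease progression refers to.

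The cost is protocol wording and attendance at visits already planned. There are three limits. Values after removal may reflect changed care and need cautious reading even when flagged. The second-session contrast is not recovered if that session is not given. Patients who withdraw consent remain missing under any rule.
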